9.3. Enrollment and Randomization

Subjects are considered enrolled in the trial after informed consent and a randomization code (kit number) is provided. To enroll and randomize a patient, the enrolling investigator or designee confirms eligibility criteria is met and enters the required data into the Electronic Data Capture (EDC) portal. After all required data for entry is entered and no violations are present, the EDC will provide a randomization code / kit number.

9.4. Subject Tracking and Loss to Follow-up

The local study team will collect extensive contact information on each subject from multiple sources to facilitate future attempts to contact the individual by phone for long-term outcomes assessment. To attain a high rate of long-term follow up (>90%), the study team will request multiple phone numbers (home, cell phones, pagers, etc) and addresses from the subject and his/her relatives, friends, primary doctor (if available), clergy and clinics. At the time of consent and enrollment, proxy respondents will be asked to provide the telephone number of the place where the subject will likely reside following discharge. At the time of hospital discharge, each subject's disposition will be noted (nursing home, rehabilitation facility, another acute care hospital, subject's home, relative's home, etc) so plans can be made for long-term outcomes telephone follow-up. Date of birth (used for death records and tracking patients) will also be obtained and kept with the secure subject ID key.

Subjects cannot be deemed "Lost to Follow-Up" (LTF) without Clinical Coordinating Center (CCC) approval. The site investigator or long-term outcomes assessment team must present a case to the CCC that includes the efforts exerted to locate the study subject. Investigator may be asked to continue their efforts prior to approval.

10. Study Procedures, Assessments and Data Collection

10.1. Data Collection and Timelines

The Data Coordinating Center (DCC), CCC or its designee will instruct the study site regarding data capture procedures on electronic and/or paper Case Report Forms (CRFs). At each site, it is the Investigator's responsibility to ensure the accuracy, completeness, and timeliness of the data reported for each patient. Source documentation supporting the data should indicate the patient's participation in the study and should document the dates and details of study procedures, adverse events, and patient status.

The Investigator, or designated representative, should complete data entry as soon as possible after information is collected, preferably on the same day that a study patient is seen for an examination, treatment, or any other study procedure. Any outstanding entries must be completed immediately after the final examination. An explanation should be given for all missing data. The Investigator must sign and date the Investigator's Statement that will be supplied to endorse the recorded data.

10.2. Schedule of Events

In this section, the study day terminology does not correspond to calendar days, but reflects how the data is organized in the electronic data capture (EDC) system.

SCHEDULE OF EVENTS	Enrollment & Randomization	DAY 1	DAY 2	DAY 3	DAY 4	DAY 5	ICU D/C	HOSP D/C	DAY 30	DAY 180
Procedure										
Eligibility Verification	Х									
Informed Consent	Х									
Randomization	Х									
Study Drug Admin ^a	Х	Х	Х	Х	Х					
Demographics	Х									
Anthropometrics	Х									
Source of Admission	Х									
History and Physical ^b (including comorbidity)	Х									
Respiratory support ^b	Х	Х	Х	Х	Х	Х	Х	Х	0	
Vasopressor Use (each agent and dose) ^b	Х	Х	Х	Х	Х	Х	Х	Х	0	
APACHE II°	Х									
SOFA Score ^c	Х	Х	Х	Х	Х	Х				
Vitals ^b	Х	Х	Х	Х	Х	Х				
GCS	Х	Х	Х	Х	Х	Х				
RASS ^d	Х	Х	Х	Х	Х	Х				
CAM-ICU ^d	Х	Х	Х	Х	Х	Х				
Hematology (platelets)	А	А	А	А	А	А				
Chemistry (T.bili, creatinine)	А	А	А	А	А	А				
Lactate	А	А	А							
Coagulation	А									
Pregnancy Test ^e	Х									
Central Research Labs ^f	Х	Х	Х	Х	Х					
Antimicrobial Therapy ^b	Х						Х	Х	0	
Infection Source Datab	Х						Х	Х		
Healthcare Location	Х	Х	Х	Х	Х	Х	Х	Х	0	С
Adverse Event Monitoring										
Potentially Associated	Х	Х	Х	Х	Х	Х	Х	Х	0	
Serious	Х	Х	Х	Х	Х	Х	Х	Х	0	
Subject Completion and Follow-up										
Vital Status	-						Х	Х	0	С
Renal Replacement Free Days		1						Х	0	
VVFD		1						Х	0	
Neuro-psychological Battery										С
V - Doutous of her study site										

X = Performed by study site

A = Collect if available

O = Only performed by study site if patient remains hospitalized at 30 days

C = Performed by Central Long-Term Outcomes Team

^a Note: patients that receive ≤ 3 administrations of study drug/placebo on Enrollment & Randomization day, will complete the last dose(s) on day 4 (if they remain in the ICU that long)

^b Data will be abstracted from Electronic Medical Record (EMR). Abstracted data will include baseline data, and daily data. For baseline data, use most abberant elements from the 24 hours preceding the time of randomization. For daily values, use data from as close to 8 a.m. as is possible up to day 5 or ICU discharge (whichever occurs first). Vasopressor doses will only be recorded at time of randomization. After randomization day, only report the use of vasopressors or not (yes/no).

^c Data elements collected via REDCap; score calculated centrally.

^d Performed by research staff, at time of randomization and days 1-5 or ICU discharge (whichever occurs first).

^e Pregnancy test (serum or urine), documentation of surgical sterilization or menopausal required for eligibility. If not performed as standard of care, patient will not be eligible ^f Central Research Labs will only be collected at designated site

10.3. Laboratory assessments

Though specific laboratory data or results are not required for eligibility, it is **expected** that various laboratory tests will routinely be performed by the treating clinical team. When available, recorded lab data should be from values as close to 8 a.m. daily up to day 5 or ICU discharge (whichever occurs first, see schedule of events). These tests include, but are not limited to: complete blood count including platelets with or without differential, chemistry including creatinine and total bilirubin, serum lactate, coagulation studies, blood cultures, procalcitonin (PCT), C-reactive protein (CRP), urinalysis, and arterial or venous blood gas.

Note, women of child bearing age who have not undergone a sterilization procedure cannot be considered for enrollment unless the clinical teams has demonstrated they are not pregnant via a negative pregnancy test as part of routine care.

Due to the potential for errors in some point of care glucometers in the setting of high serum vitamin C concentrations (see section 3.5), participating sites will be required to measure glucose using a point of care device that has been validated for use in the setting of high vitamin C concentrations ⁸¹, or use devices validated for high vitamin C concentrations⁸¹ in their critical care or central laboratory. If glucose is measured in a critical care of central laboratory, approximately one milliliter of blood will be obtained from an artery or vein. The number of blood draws will depend on each patient's needs and the number of glucose measurements clinical care providers order. For sites that do not have a valid point of care glucometer, and do not want to use their critical care or central laboratory, Nova Biomedical has agreed to loan sites two Nova StatStrip devices, a charging station, and test strips. Nova Biomedical will also provide on-site training in the use of the devices. Of note, use of loaned devices in this study will require the use of venous or arterial (approximately one drop of blood per measurement) samples and NOT fingersticks. The number samples will depend on each patient's needs and the number of glucose measurements clinical care providers order. Loaned StatStrip glucometers will be validated on site as detailed in the "Procedure Manual" uploaded with this application. Sites that already use a glucometer that has been validated for use in the setting of high vitamin C concentrations should measure glucose according to their usual protocol.

10.4. Clinical Assessments and Procedures

Baseline Data - At enrollment, basic information about disease characteristics and the subject, including common sepsis and research related variables will be collected. Examples include:

- Demographics
 - Age
 - Race/Ethnicity
 - o Gender
 - Education
- Anthropometrics
- Source of Admission
- Comorbidities and Medical History
- History and Physical (brief physical exam findings)
- APACHE II (ICU mortality) using the most aberrant data from the 24 hours preceding the time of randomization

- SOFA Score
- Vasopressor requirements
- Respiratory and ventilator support requirements
- Total volume of fluid resuscitation
- Presumed infection source and organism
- Initial antimicrobial therapy
- CAM-ICU

Daily Measurements and Physiologic Data:

Use data that is obtained as close to 8 a.m. each day while the patient is in the ICU up to day 5.

- Vital Signs (MAP, HR, RR, and Temp)
- CAM-ICU Score
- SOFA Score
- Study Drug Compliance

Additional Measures to be determined and collected at time of ICU discharge and/or Hospital Discharge:

- Daily Vasopressor Requirements
- Daily Ventilator / Respiratory Support Requirements
- Antimicrobial therapy
- Final infectious source data
- Location and/or disposition

Outcome Assessments – The primary outcome measure is VVFD at 30 days (+/-3 days) after randomization. Vasopressor and ventilator-free days will be determined by recording all start and stop days of these measures. Additional measures will include renal replacement therapy (RRT) free days and determination of subject's vital status. These will be assessed at ICU discharge, and hospital discharge or day 30 (whichever comes first). The final study visit for individual sites will be the time of hospital discharge or day 30 (whichever comes first). For patients discharged prior to day 30, status at discharge will be assumed to reflect outcome at day 30.

Long Term Outcome Assessments Sub-Study - Explicit subject consent for participation in long term telephone follow-up will be sought for all patients at all sites. Participation in long term outcome assessments is not required for participation in other aspects of the VICTAS study. Subjects who participate will be compensated fifteen dollars. In these participants a diverse array of neurocognitive outcomes will be assessed approximately 6 months after patient discharge. Evaluations will be done using a specially-designed battery of tests that evaluates key aspects of functioning and behavior and will be administered via phone by the Vanderbilt Long-Term Outcomes team, which will serve as the coordinating center for these follow-up assessments. The battery, which takes about 40 minutes to complete, will assess cognition, mental health (depression and PTSD), quality of life, and employment - all of which have been shown to be adversely affected in between one third and two thirds of survivors of sepsis. This battery has been successfully used by researchers in multiple studies at Vanderbilt Medical Center and elsewhere - it is well tolerated by patients, easy to administer and to understand, and is very sensitive to the detection of even minor difficulties. Tests comprising the battery (*by domain and name*) are as follows:

Cognition: Attention (Digit Span), Delirium (Telephone Confusion Assessment Method), Executive Functioning (Hayling Test), Language (Controlled Oral Word Association Test or COWA), Memory (Paragraph Recall from the Wechsler Memory Scale IV), Orientation (Telephone Interview for Cognitive Status), Reasoning (WAIS-IV Similarities)

Functioning: Activities of Daily Living (Katz ADL), Employment (Employment Questionnaire), Instrumental Activities of Daily Living (Functional Activities Questionnaire)

Mental Health: Mental Health: Depression (PROMIS Depression 6), PTSD (Posttraumatic Stress Disorder - 8)

Quality of Life: EuroQol, 5 dimension (EQ5D)

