The primary outcome for this trial is the number of consecutive days free of vasopressors and mechanical ventilation (VVFD) in the first 30 days after start of the Study Intervention, recorded to the nearest day. Ventilator and vasopressor free days will only accrue from the last date the patient was free of both ventilator and vasopressor support. Patients who die are scored zero VVFD, and patients who return to ventilator support or vasopressor support (as defined in the inclusion criteria) will have the VVFD count reset to zero days.

Secondary Outcomes

Secondary outcomes will be mortality at 30 days, ICU mortality, mortality at 180 days, length of ICU stay, length of hospital stay, and long-term emotional and cognitive outcomes at 180 days.

6. Study Design

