For the primary outcome measure (VVFD), we will use an adaptive strategy with assessments at 500, 1000, 1500, or 2000 subjects randomized to either the TP or CP. When the data are sufficiently strong on the primary endpoint (VVFD), the trial may select a smaller sample size, but when necessary (e.g. for a moderate effect), the trial may continue to a larger sample size.

The overall Type I error rate for the trial is controlled at 2.5%. The early interims at N=200, 300, 400 are designed to conservatively spend alpha so that 2.4% remains for the analysis at N=500 (or beyond).

Anticipated alpha expenditures at all interim analyses, determined through clinical trial simulation, are as follows:

Interim Analysis	Alpha Spend
N = 200	0.0002
N = 300	< 0.0001
N = 400	0.0003
N = 500	0.010
N = 1000	0.0026
N = 1500	0.0033

The power estimates used for sample size selection if the trial progresses to N=500 and beyond were also determined through clinical trial simulation, and take into account both the primary outcome of VVFD and the secondary mortality outcome. Indeed, these two outcomes are inter-related, with our primary efficacy endpoint (VVFD) representing a combination of treatment effect on mortality (all deaths are recorded as zero VVFD) and effect on vasopressor and ventilator support dependence in survivors. Full details of these simulations, over a wide range of assumptions, may be found in a separate document entitled *VICTAS Trial Adaptive Design Report*.

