11.4.1. Primary Efficacy Endpoint

The primary efficacy endpoint is vasopressor and ventilator-free days (VVFD) in the first 30 days after start of treatment. The endpoint will be recorded to the nearest day. Subjects who die will be scored zero days, even if there is a period during which the subject is alive and free of vasopressors and mechanical ventilation. Subjects who must return to ventilation and/or vasopressors will have their counters reset at zero days. If the trial reaches N=500 or more, the primary analysis is a Wilcoxon rank-sum test (also known as a Mann-Whitney U test), which will be performed using a one-sided alpha of 0.022. If the study is extended beyond N=500, then the final analysis on VVFD requires p<0.022. This p-value threshold was selected through simulations in order to control type I error and account for the multiple analyses at N=500, 1000, 1500 and 2000.

The primary analysis will be performed on the ITT population. A sensitivity analysis will be performed on the PP analysis set.

For subjects with missing data on the primary endpoint, a "last status carried forward" approach will be used. If a subject was last seen on either vasopressors or mechanical ventilation, it is assumed that the subject remained so, and is imputed to a value of zero VVFD. If the subject was last seen off of vasopressors and mechanical ventilation and is not known to be dead, it is also assumed that the subject remained so in the remainder of the 30-day period.

VVFDs will be tabulated by arm and presented graphically by histograms and cumulative distribution functions.

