The Vanderbilt Long-Term Outcomes team will work closely with local coordinators to obtain contact information enabling them to contact patients. Specifically, addresses, multiple telephone numbers, and extensive contact information (both for patients and for family members or friends who can assist us in locating patients) will be obtained and will be shared in the EDC database which will be accessible in "real time" to Vanderbilt coordinators. Using well established strategies and "best practices" such as we've described above (i.e. obtaining multiple points of contact, building relationships with patients early in the process, etc.), we anticipate successfully assessing at least 90% of all eligible patients. Follow-up models similar to those described here have been used across many multi-site outcome studies and IRB approval for such studies has always been obtained.

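### Day-30 status is taken from discharge status, so 30-day mortality as sites collect it is in-hospital death to day 30, and no rule lets a later-learned death update it

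*Combined protocol and SAP*

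**What the plan says.** Section 10.4 (Outcome Assessments) ends site follow-up at hospital discharge or day 30, whichever is earlier, and adds: "For patients discharged prior to day 30, status at discharge will be assumed to reflect outcome at day 30". The schedule in section 10.2 agrees. Vital status and VVFD carry the code O at day 30, defined as "O = Only performed by study site if patient remains hospitalized at 30 days".

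The endpoint is nevertheless called mortality at 30 days (sections 4 and 5), and section 6.2 places the final outcome 30 days after enrollment.

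Other passages bear on deaths after discharge:

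- Section 5: "Patients who die are scored zero VVFD". Section 11.2: "all deaths are recorded as zero VVFD".
- Section 11.4.1 carries off-support status forward under a condition: "If the subject was last seen off of vasopressors and mechanical ventilation and is not known to be dead". This is the missing-data rule for VVFD. Section 11.4.2, on mortality, has no counterpart.
- Section 10.2 has the central long-term outcomes team check vital status at day 180. That team's telephone follow-up is optional (section 10.4) and in English only (section 13.3).
- Section 9.4: "Date of birth (used for death records and tracking patients) will also be obtained". No search procedure or time point follows.
- Section 11.4 waits for enrolled subjects to complete follow-up, without saying whether that means day 30 or day 180.

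**The concern.** A death between discharge and day 30 is a 30-day death by the endpoint's name, but a survivor by the rule in section 10.4. If the patient left off support, the VVFD score also stays positive. If the patient left on support, section 11.4.1 already gives zero VVFD, and only the mortality record is wrong.

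Mortality alone decides the looks at N=200, 300 and 400. From N=500 it is the key secondary test, made only after VVFD succeeds. Deaths also set the primary endpoint to zero. One uncollected fact therefore reaches every confirmatory test. Missing the same share of deaths in both arms shrinks the risk difference and costs power. Missing different shares would bias the comparison.

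**Working it through.** **Reading the text.** Sections 10.2 and 10.4 agree with each other, so discharge status is the operating rule. Section 11.4.1 allows a known death to count for VVFD, but gives no way of learning of it and does not cover mortality. Section 10.5 imputes failure when an endpoint is missing because of death. Under section 10.4, however, the discharged patient is not missing but an assumed survivor. The day-180 check and death records could reveal such deaths, yet nothing links them to day-30 status.

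**The plan's own power figure.** Section 11.2 claims over 90% power for a 20-point difference at one-sided 0.001, giving neither a control rate nor an N in that sentence. Assume 40% v 20% (the pilot's historical controls had 40.4%) and N=400, so n=200 per arm:

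Power = Φ{[d − z·√(2p̄(1−p̄)/n)] / √[(pC(1−pC) + pT(1−pT))/n]}

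With d=0.20, p̄=0.30 and z=3.090: (0.20 − 3.090×0.04583)/0.04472 = 1.31, so power is 90.4%. The claim is reproduced.

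**Missed deaths, equal shares.** Let m be the share of 30-day deaths that occur after discharge and r the share of those later recovered. Both rates are multiplied by 1 − m(1 − r). The documents give no m, so 10, 20 and 30% are assumptions. Example with m=20%, r=0: rates are 32% and 16%, and (0.16 − 3.090×0.04271)/0.04195 = 0.67, so power is 74.8%.

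| N=400, 40% v 20%, one-sided 0.001 | m=0 | 10% | 20% | 30% |
|---|---|---|---|---|
| none recovered | 90.4% | 83.8% | 74.8% | 63.8% |
| 90% recovered | 90.4% | 89.9% | 89.3% | 88.7% |

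The 90% is also an assumption. Section 13.3 says "we anticipate successfully assessing at least 90% of all eligible patients", but that concerns the telephone assessment, not the finding of deaths.

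**From N=500, with the gatekeeping order applied.** These are fixed-N simulations: a tie-corrected Wilcoxon test at one-sided 0.022, then mortality at one-sided 0.024, counted only if VVFD succeeds. The support model is assumed: survivors' last support day is 1 + floor(Gamma(shape 1.2, scale 4.5)), capped at 30. Every missed death takes a survivor's score, and none is recovered.

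| Mortality power | m=0 | 10% | 20% | 30% |
|---|---|---|---|---|
| 40% v 20%, N=500, effect on deaths only | 97% | 94% | 86–88% | 76% |
| 25% v 20%, N=2000, effect on deaths only | 45% | 37% | 29% | 22% |
| 25% v 20%, N=2000, support also shortened (scale ×0.85) | 76% | 70% | 64% | 57% |

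The 86–88% entry is the spread between simulation runs. In the last row VVFD almost always succeeds (98 to 97%), so the closed-form mortality power without the VVFD condition is a check: 75.8, 70.1, 63.7 and 56.8%.

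**Type I error.** With 25% mortality in both arms and 20% of deaths missed in both, hierarchical mortality error stays within the nominal 2.4%: 0.7% (N=500) and 0.8% (N=2000) with no VVFD effect, and 2.0% and 2.3% if treatment speeds recovery (×0.85). Now let treatment speed recovery, leave mortality unchanged, and make the missed shares differ:

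| Missed, treatment v control | N=500 | N=2000 |
|---|---|---|
| 12% v 10% | 2.9% | 4.2% |
| 20% v 10% (extreme) | 8.4% | 26.7% |
| 20% v 10%, 90% recovered | 2.3% | 3.2% |

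**Timing of later information.** Assume constant accrual at 500/36 = 13.9 a month (section 6.4) or 20 sites × 2 = 40 a month (sections 6.4 and 9.2). When the 400th patient reaches day 30, those enrolled in the preceding 150 days (4.93 months) have not reached day 180: 68 or 197 patients, which is 17% or 49% of 400. Whether day-180 information can help thus depends on what section 11.4 means by completed follow-up.

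**The case against.** The assumption in section 10.4 is stated openly. Known deaths already override carry-forward for VVFD, a day-180 vital-status check is planned, and date of birth is kept for death records. A missed early stop does not end the trial. The shares, the support model and the ×0.85 factor come from no passage, and the separate Adaptive Design Report is not available. All of this stands, and it limits the point.

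Three stronger readings are tempting, and the documents support none of them:

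- *That the plan contradicts itself by scoring known deaths as survivors.* Section 10.4 can be read as a default for patients about whom nothing more is heard. It needs reconciling with section 11.4.1, but is not a firm contradiction.
- *That the rule inflates type I error in general, including for VVFD when treatment does nothing.* In a randomized, double-blind trial with no effect on death or recovery, nothing makes the missed share differ systematically by arm. The only plausible route is earlier discharge on treatment, which presupposes a real effect on recovery, and blinding limits other routes.
- *That the N=400 loss is a loss for the trial.* The design continues to 500 and beyond, and most of the power for so large an effect is regained there.

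**Conclusion.** The point holds as a defect in how the endpoint is defined and updated. As sites collect it, 30-day mortality is in-hospital death to day 30, and no passage says that a death learned later revises it. This should be fixed, because mortality drives the early looks and enters the primary score.

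The size depends on a share of post-discharge deaths that the documents do not give. Over 10 to 30%, equal in both arms and none recovered, the loss at N=400 is about 7 to 27 points, and for a 20-point effect the consequence is mainly a later stop. The loss matters more for a moderate effect: for 25% v 20% at N=2000, about 8 to 23 points if only deaths are affected, or 6 to 19 if support is also shortened. Figures that depend on VVFD are at the upper end, because every missed death is given a survivor's score. With 90% recovery the N=400 loss is under 2 points. Error inflation needs unequal shares and is small at 12% v 10%. None of the power loss is additional if the design report already uses in-hospital rates.

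**What to change.** Replace the sentence in section 10.4 with: *Any death on or before day 30, learned from any source before database lock, counts as a 30-day death and scores 0 VVFD; discharge status is used only when vital status to day 30 remains unknown.*

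Then:

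- Record the date of death at the day-180 vital-status check and in any death-record search, and use it to update day-30 status.
- State in section 11.4 which follow-up must be complete before the final analysis.
- Add a sensitivity analysis for patients whose day-30 status stays unknown, for example counting them as dead with 0 VVFD.
- Optionally, add a brief day-30 record or telephone check, within consent, for patients discharged alive. At 20–25% mortality and if every survivor is checked, that is 500 × 0.75 to 0.80 = 375 to 400 checks at N=500, and 1500 to 1600 at N=2000.

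If day-30 status after discharge is not to be obtained, rename the endpoint in-hospital mortality to day 30.

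The cost is changed wording, a small abstraction effort, and possibly some delay if the analysis waits for later vital-status information.

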11.4.3. Additional Efficacy Endpoints

The following endpoints will be analyzed as supportive evidence of treatment benefit. The tests will not be included in the gatekeeping strategy, so that type I error will not be adjusted for multiple testing:

Other outcomes Mortality at 180 days Length of ICU stay Length of hospital stay Physical, emotional and cognitive outcomes at 180 days

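### Long-term cognitive, emotional and physical outcomes are named for day 180, but Section 10.4 times the battery from discharge, so the assessment day moves with length of stay

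*Combined protocol and SAP*

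**What the plan says.** Three places name the outcomes at a fixed time. The Executive Summary and Section 11.4.3 list "Physical, emotional and cognitive outcomes at 180 days". Section 5 lists "long-term emotional and cognitive outcomes at 180 days", leaving out the physical domain. The schedule of events (Section 10.2) enters the neuropsychological battery under day 180, in the same column as vital status, with the code "C = Performed by Central Long-Term Outcomes Team".

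Section 10.4, describing the long-term sub-study, gives a different clock: "In these participants a diverse array of neurocognitive outcomes will be assessed approximately 6 months after patient discharge".

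No section states where day 180 starts, gives it a window, or reconciles the two timings. The plan does both for day 30: "The primary outcome measure is VVFD at 30 days (+/-3 days) after randomization". Section 5 also lists "length of ICU stay, length of hospital stay" among the secondary outcomes. For deaths, Section 10.5 assigns secondary endpoints the worst possible value.

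**The concern.** Discharge happens after randomisation, and its date depends on how quickly organ support ends, which is what the therapy is meant to change. A call timed from discharge therefore reaches each patient at a different time since randomisation, and the delay is longest for survivors with the longest stays. The battery covers cognition, mental health, daily functioning, employment and quality of life. If scores in these domains change as patients recover, time since the illness is mixed into the comparison.

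Results reported as 180-day outcomes could then have been collected at dates that vary by weeks and are linked to another trial outcome. Two outcomes carrying the same 180-day label could also treat the same patient differently when a death occurs late.

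**Working it through.** The plan states no figure to reproduce here. The check compares the sections and then does simple date arithmetic.

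**1. Which origin does day 180 have?** None is stated. Section 10.4 ties day 30 to randomisation. Section 10.2 puts the battery in the same column as 180-day vital status. Both point to randomisation, but this is an inference. Section 10.2 also warns that "the study day terminology does not correspond to calendar days".

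**2. Which discharge?** Section 10.4 does not say. Section 9.4 records disposition at hospital discharge "so plans can be made for long-term outcomes telephone follow-up", so hospital discharge is the natural reading. The dispositions listed there include rehabilitation and another acute care hospital, so two staff members could start the clock on different dates for one patient.

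**3. Assessment day under the discharge clock.** Formula: assessment day = days from randomisation to discharge + 6 months. The documents give no length-of-stay figures, so the discharge days below are assumptions. Six months is taken as 180 days, and also as 365.25 / 12 × 6 = 182.6 days.

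| Discharge day (assumed) | 6 months = 180 d | Late against day 180 | 6 months = 182.6 d | Late against day 180 |
|---|---|---|---|---|
| 7 | 187 | 7 d (3.9%) | 189.6 | 9.6 d (5.3%) |
| 30 | 210 | 30 d (16.7%) | 212.6 | 32.6 d (18.1%) |
| 60 | 240 | 60 d (33.3%) | 242.6 | 62.6 d (34.8%) |

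Over a wider assumed range of 5 to 90 days, with 182.6 days, the call is about 8 to 93 days late (4% to 51%). With a fixed day-180 anchor the target is day 180 for everyone.

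**4. Difference between arms.** The constant 6 months cancels, so the difference in mean assessment day equals the difference in mean stay among those assessed. For an assumed difference of 1 to 5 days, the shift is 1/180 = 0.6% to 5/180 = 2.8% of the nominal interval.

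**5. Deaths.** Take a patient discharged on day 30, with a call due at about day 210, who dies after day 180 but before that call. For 180-day mortality this patient is a survivor. For the battery, Section 10.5 gives the worst value. With a day-180 target and the rule limited to deaths up to day 180, the two outcomes agree.

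**The case against.** The strongest case on the other side has five parts.

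- **The conflict rests on an inferred origin.** This stands in part. If day 180 was meant from discharge, the fault is an undefined anchor and not a contradiction. The assessment day would still move with length of stay.
- **The schedule of events is operational too.** This stands. The outcomes team may follow its day-180 column, and the discharge timing is only approximate. A reader might infer that no patient will be assessed at day 180. The documents do not support that, because they do not show which text prevails, and short-stay patients could fall close to day 180 in any case.
- **A discharge anchor is defensible for some domains.** For employment and instrumental daily activities, equal time since discharge has some logic, and a day-180 anchor makes time since discharge vary instead. This is a real trade-off. But a discharge clock is not what the endpoint name says, and it starts at an event that treatment may affect.
- **A reasonable window would admit many of the timings complained of.** An illustrative window of 30 days either side runs from day 150 to day 210 and contains the day-187 and day-210 examples. This stands, and it limits the size of the problem. What the fix removes is the systematic tie between target date and stay.
- **The stakes are small.** Participation in the sub-study needs separate consent, the battery is given only in English (Section 13.3), and these endpoints are supportive, outside the gatekeeping and not adjusted for multiplicity (Section 11.4.3). This stands.

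A reader might also infer a material bias between arms. The documents give no length-of-stay data and no rate of change in the scores, so that cannot be shown. If treatment shortens stay and scores improve with time, treated patients would be called earlier, which would work against the therapy. Nor does a late death leave the battery without a score: Section 10.5 assigns the worst one. And these are not the trial's only patient-centred outcomes, since mortality is one as well.

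**Conclusion.** The timing sentence in Section 10.4 is wrong as written. It departs from the endpoint name in three sections and from the schedule, and it ties the assessment date to a post-randomisation event that is itself a listed outcome. Under the assumed stays of 7 to 60 days, and 6 months taken as 180 days, patients would be assessed 7 to 60 days after the nominal date. That spread between patients is the main effect. A difference between arms is possible but probably only days, and its size is an assumption. The number of patients who would die between day 180 and a discharge-timed call cannot be estimated from the documents.

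The conclusion rests on two inferences: that day 180 runs from randomisation, and that discharge means hospital discharge. The impact is modest. No primary or key secondary analysis, alpha, power or stopping rule is affected. The change is still worth making, because it is small and leaves the endpoint with one meaning.

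**What to change.** In Section 10.4, set the target for the battery at day 180 after randomisation, with one stated window in days for both arms, whether or not the patient has left hospital or rehabilitation. Calls should aim for day 180 itself, so that the window does not let the link to length of stay back in. Its width is for the sponsor to choose; 30 days either side is only an example.

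State the same origin in the Executive Summary, Section 5, the Section 10.2 schedule and Section 11.4.3, and make the list of domains agree. In Section 10.5, apply the worst-value rule for the battery only to deaths up to day 180. Record the date of each assessment and tabulate time since randomisation by arm.

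The cost is one changed sentence in Section 10.4, matching edits elsewhere, and a new call date in the outcomes team's tracking. It adds no assessments and leaves sample size, power and alpha unchanged. The downside is that some long-stay patients will be called sooner after discharge, or while still in a facility.
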